#### **Stratified analysis**

The same two-stage analysis will be carried out for the following strata:

- Age groups:
  - seasonal vaccine < 75 years and > 74 years.
  - pandemic vaccine age groups targeted for pandemic vaccination.
- Presence or absence of high risk conditions.
- Time (early influenza season, peak, late influenza season).
- Virus type.
- Vaccine brand.
- Target groups for pandemic influenza vaccine.

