# 1 Background

Influenza viruses constantly evolve, vaccines are reformulated every year. Therefore, vaccine effectiveness (VE) estimates from previous years cannot simply be carried over to subsequent years.

Conducting annual influenza VE estimates at the European level right at the beginning of a seasonal influenza epidemic/pandemic and monitoring VE along the course of the epidemic/pandemic is crucial in order to:

- decide on recommendations for the use of the vaccine;
- target complementary or alternative public health measures (e.g. antivirals) for segments of the population where the vaccine is less effective;
- allow more precise estimates of the impact of current vaccination strategies on the burden of disease to support vaccination campaigns;
- trigger further investigations on seasonal and pandemic vaccines (improve composition, use of adjuvants, need for booster doses);
- better manage and respond to expected reports of vaccine failures (especially during a pandemic); and
- counterbalance the reports of adverse events following immunisation by providing elements for adequate risk management and cost-effectiveness analysis.

The recent occurrence of the A(H1N1)v pandemic augments the importance of obtaining reliable and early vaccine effectiveness estimates for the pandemic vaccine. It takes approximately four to six months for the first supplies of strain-specific vaccines to become available once a new strain of influenza virus is identified and isolated. Consequently, by the time the vaccines are first administered, the virus already circulates and VE results are needed rapidly. In addition, vaccine availability is likely to increase over time – depending on vaccine production output and the licensing of additional vaccines, which means that IVE measurements need to be repeated over time during the pandemic. VE studies may help determining if the seasonal influenza vaccination is effective or interacts with pandemic vaccine in protecting against the A(H1N1)v virus.

Currently, only observational studies can be used to provide real-time estimates of influenza VE in Europe.

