#### Stratified analysis

Analysis will be stratified according to:

Seasonal vaccine:

- Age groups < 75 years and > 74 years.
- Presence or absence of high-risk conditions.
- Time: early influenza season, peak, late influenza season.
- Virus strain.

Pandemic vaccine:

- Vaccine brand.
- Time: different periods defined by pandemic vaccine availability.
- Target groups.

A sufficient sample size should be planned in order to ensure enough individuals in each stratum for a precise estimate. For example, assuming a vaccination coverage of 50% and a VE of 60%, studies should aim to have at least 90 cases and 90 controls in each of the strata. Effect modification will be assessed comparing the OR across the strata of the baseline characteristics. Confounding will be assessed by comparing crude and adjusted OR for each baseline characteristic.

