## Two-stage pooling approach

If adequate sample size by study is achieved to obtain an adjusted OR, then a two-stage approach to pooled analysis will be taken. Studies considered to be heterogeneous will not be included in the two-stage model.

Study-specific adjusted ORs and standard errors for the effect of current influenza vaccination obtained from the individual studies will be combined in a model that incorporates random effects of the studies, to account for unmeasured country- and study-specific factors that differ between studies.

The study-specific exposure-disease effects (ORs) will then be weighted by the inverse of their marginal variances. The marginal variance is the sum of the individual study-specific variances and the variance of the random study effects ( $\tau^2$ ). This will give the pooled odds ratio and standard error. See Annex 6 for an example of Stata syntax.

$$\log(OR_R) = \frac{\mathbf{\mathring{a}} \ w_i \ast \log(ORi)}{\mathbf{\mathring{a}} \ w_i \ast}$$
$$wi^* = \frac{1}{vi + t^2}$$

The study-specific ORs and their CIs, along with the pooled odds ratio, will be presented graphically in a forest plot. This model will also be compared against a two-stage analysis with fixed study effects, to assess the effects of model assumptions.

If despite the common protocol, covariates were not uniformly collected in the different studies, then an analysis will be carried out excluding certain studies, and a comparison to the analysis including all studies will be made. In a different scenario, analyses can also be carried out excluding certain study participants for whom variables were collected differently.

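### Pooled VE is estimated stratum by stratum and no within-country contrast is pooled, so a difference between pooled strata can be a difference between countries, or a real one can be missed

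*Protocol*

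**What the plan says.** Annex 3, under Two-stage pooling approach, defines the pool. "Study-specific adjusted ORs and standard errors for the effect of current influenza vaccination obtained from the individual studies will be combined" in a random-effects model, chosen "to account for unmeasured country- and study-specific factors that differ between studies". The route is conditional: "If adequate sample size by study is achieved to obtain an adjusted OR, then a two-stage approach to pooled analysis will be taken". It also states: "Studies considered to be heterogeneous will not be included in the two-stage model".

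Annex 3, under Stratified analysis, then repeats this pool by stratum: "The same two-stage analysis will be carried out for the following strata". The strata are age group, high-risk condition, time, virus type, vaccine brand and pandemic target group.

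Section 3.13 handles effect modification under Individual study analysis. There, "Effect modification will be assessed comparing the OR across the strata of the baseline characteristics", and the multivariable model tests interactions by likelihood ratio or Wald test at the 5% level.

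At the pooled level, the only interaction test is study by covariate (Annex 3, Small sample sizes), and its purpose is to check the one-stage model. The example syntax in Annex 6 has no vaccination-by-stratum term.

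The protocol also says that target groups may differ by country (sections 3.2 and 3.9). Below Table 3 it says that numbers by brand will depend on market share.

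**The concern.** Section 2.2 makes VE by risk group and by brand objectives. Section 1 says the results should help target other measures at "segments of the population where the vaccine is less effective". Readers will therefore compare the pooled stratum VEs with each other, and two things can go wrong.

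- **Country mix.** Each pooled stratum VE is a weighted average over the countries that supply that stratum. If countries differ in VE and supply the strata unequally, the comparison mixes effect modification with country differences.
- **Precision.** Each stratum interval carries the between-study variance. Where the same country contributes to both strata, its country effect is shared and cancels in a within-country contrast. Setting two separate pools side by side counts it twice.

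A brand or risk group could then look worse because of where it was studied, or a difference present in every country could be missed.

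**Working it through.** **1. The plan's own figure.** Table 2 gives 89 cases and 89 controls at 50% coverage, OR 0.4, power 0.8 and alpha 0.05. Vaccination among cases is 0.4 × 0.5 / (0.5 + 0.4 × 0.5) = 0.286, against 0.5 in controls. The two-proportion formula gives 80.4 per group, or 89.4 with continuity correction, which agrees with Table 2. This size serves the VE within one stratum, not a contrast between strata.

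**2. What one study can show.** The Woolf variance of a log OR with n cases and n controls is 1/(n p₁) + 1/(n(1−p₁)) + 1/(n c) + 1/(n(1−c)), where p₁ is vaccination among cases and c is coverage. At n = 90 and c = 0.5 it is 0.0989 for OR 0.4 and 0.0903 for OR 0.7. The SE of the difference is √(0.0989 + 0.0903) = 0.435. The true difference is ln(0.7/0.4) = 0.560, so z = 1.29 and power is about 25%. Interaction tests in single studies of this size are weak unless they are pooled.

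**3. Country mix, with no effect modification in any country.** Assumed: five studies with ORs 0.30, 0.35, 0.45, 0.55 and 0.60 (SD of the log OR about 0.29), the same OR in both strata of each study, and 50% coverage. Each stratum is pooled by DerSimonian-Laird at expected values. Sizes are cases, with as many controls.

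| Contribution to stratum 1 / stratum 2 | Pooled VE | Log OR difference (SE) | z |
|---|---|---|---|
| Studies 1-3 / all five, 120 each | 64% / 56% | 0.19 (0.21) | 0.93 |
| Studies 1-3 (150, 150, 90) / studies 3-5 (90, 150, 150) | 65% / 46% | 0.44 (0.21) | 2.05 |
| All five, 150, 150, 90, 40, 40 / reversed | 61% / 50% | 0.27 (0.19) | 1.37 |

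The true difference is zero in each row.

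A simulation with assumed country VEs of 70, 70, 40 and 40% and no effect modification gave these mean log OR differences:

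- same mix in both strata: 0.00;
- sizes 300, 300, 90, 90 against the reverse: 0.14 (pooled within-study contrast 0.00);
- countries 1-3 against 2-4: 0.23 (within-study 0.00);
- disjoint countries: 0.69, a ratio of ORs of about 2, significant in 46% of runs, with no within-study estimate possible.

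With equal VE in all countries, an unequal mix gave 0.00.

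**4. Precision, with all five studies in both strata at 90/90, OR 0.4 against 0.7.** The within-study contrast has SE √((0.0989 + 0.0903)/5) = 0.195 at any tau. Two separate pools are credited with SE √((0.0989 + 0.0903 + 2τ²)/5). The real sampling SD of their difference stays near 0.195 because the country effects cancel.

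| tau | SE, separate pools | Ratio to 0.195 | Power, separate (tau known) | Power, within-study (tau known) |
|---|---|---|---|---|
| 0 | 0.195 | 1.00 | 82% | 82% |
| 0.2 | 0.232 | 1.19 | 71% | 82% |
| 0.3 | 0.272 | 1.40 | 56% | 82% |
| 0.5 | 0.371 | 1.91 | 19% | 82% |

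Simulation with tau estimated by DerSimonian-Laird gives, separate against within-study, 54-56% against 73-75% at tau 0.3, about 31-33% against 73% at tau 0.5, and no material difference at tau 0.

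**5. False positives.** With all countries in both strata and no effect modification, comparing separate pools rejects in 1.3% of runs at tau 0.3 and 0.6% at tau 0.5, which is below 5%. With disjoint country sets (six studies, random country effects) it rejects in 6.4% and 9.5%.

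**The case against.** The strongest reply is that Annex 3 only estimates VE in each stratum, which is what the objectives ask for, and states no test between pooled strata. The sentence on comparing ORs across strata belongs to the individual study analysis, where country cannot confound the comparison. The next subsection adds interaction tests within each study. All of this is correct. A reader might infer that comparing ORs is the protocol's only method for effect modification, or that a formal comparison of pooled strata is planned. The text supports neither.

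A reader might also infer that studies enter or leave each stratum's pool one by one on size. The condition "If adequate sample size by study is achieved to obtain an adjusted OR" decides whether the two-stage route is taken; it does not say that it operates stratum by stratum. Section 3.13 tells studies to aim for 90 and 90 in every stratum, and small samples may go to a one-stage model, which Table 3 uses for the pooled interim outputs. The mix can still differ, because target groups and brands differ by country.

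The examples are built to show the problem: study ORs are sorted and availability follows that order. Only one of the three passes 1.96. Forest plots and the caution about pooled bias in section 3.15 help a careful reader.

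What remains is that the within-study interaction estimates never reach the pooled analysis, which is the only place with enough data to use them. Annex 3 fixes the pooled method itself, so this is more than a detail left for a later plan.

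**Conclusion.** The point holds in limited form. The stratum-specific pooled VEs are legitimate as description. They are a poor basis for saying that VE differs between strata when VE also varies by country, which the random-effects model allows for.

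- **Bias** needs both a VE difference between countries and a different country mix by stratum. In the constructed cases it is 8 to 19 percentage points of VE. With equal VE in all countries, or the same mix in both strata, it is zero.
- **Loss of power** needs only a VE difference between countries. At tau 0.3 it is roughly 20 percentage points (54-56% against 73-75%).
- **False positives** are not raised in general. A reader might infer that from the inflated standard error, but with all countries in both strata the rate falls below 5%. It rises when the strata come from different countries.

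Tau, the number of studies and the mixes are assumptions. The change is worth making but is not critical.

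**What to change.** Add to Annex 3, Stratified analysis:

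- The stratum-specific pooled VEs are descriptive, and the countries contributing to each stratum are listed.
- For age group, high-risk condition and time period, and for target group and brand where a country has more than one, each study estimates the vaccination-by-stratum interaction log OR and its SE in one adjusted model. For brand, this is the contrast between brands against a common unvaccinated reference. These estimates are pooled with the same random-effects command.
- A difference between pooled strata is reported as effect modification only from this pooled within-study estimate.
- Virus type is left out, because it is a property of the outcome and controls have none.
- Where strata occur in disjoint countries, the report states that stratum and country cannot be separated. No analysis repairs that case.

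The cost is a few sentences and one more coefficient per study and stratifying variable, with no new data. The downside is that countries with only one stratum do not inform the contrast, although they still count in the stratum VE.

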## **Controlling for GP effect**

Primary analysis will be carried out using simple logistic regression to obtain the individual study estimates. However, there could be a GP effect that is related both to the exposure (propensity to vaccinate) and the outcome (in terms of swabbing behaviour). To adjust for this cluster effect, a multi-level logistic regression will be carried out for each individual study with GP as a random effect. Then the two-stage model as outlined above will be used to obtain a summary VE measure, using these estimates. The same applies to stratified analyses. Point estimates and confidence intervals of the respective summary VE measures will be compared in a sensitivity analysis.

#### **Small sample sizes**

While great effort will be taken to ensure adequate sample size at individual study level, both for overall and stratified estimates, it will still be possible that small sample sizes occur, particularly when estimating early or intra-seasonal VE measures.

When sample sizes at the individual study level are too small to adequately control for confounders, individual study data can be pooled into one dataset and analysed as a one-stage model with study as a fixed effect (see Annex 6 for Stata syntax). This could provide a large enough sample size to obtain, for example, an estimate of VE with reasonable precision early in the season. The results of this analysis should be interpreted with caution, though, as it assumes not only that the underlying true exposure effect is the same in all studies, but also that the association of all covariates with the outcome is the same in all studies.

If a pooled dataset with large sample size is available (e.g. later in the season) then formal tests of interaction between study and covariate will be carried out to determine if the effect of each covariate differs across studies. This way, the validity of using a one-stage model analysis (earlier in the season) can be tested.

## Annex 4: Data flow for pooled database

#### Figure: Data flow for pooled database

Countries send their individual data to EpiConcept, according to minimum dataset guidelines.

# Annex 5: Generated/recoded variables

#### Table: Generated/recoded variables

Variable name	Туре	Values and coding	Definition
caseflu	Numeric (binary)	0 = No 1 = Yes	Indicates ILI case that is lab- confirmed for influenza.
ili	Numeric (binary)	0 = No 1 = Yes	Variable that corresponds to EU ILI case definition (coded using the symptoms in dataset).
panvaccdelay	Numeric (continuous)	Integer	Number of days between pandemic influenza vaccination date and onset date of symptoms (needs to be modified if 2 doses are required).
panvacc	Numeric (binary)	0 = No 1 = Yes	Coded as yes if >14 days between pandemic vaccination and onset of symptoms (needs to be modified if 2 doses are required).
seasvaccdelay	Numeric (continuous)	Integer	Number of days between seasonal influenza vaccination date and onset date of symptoms.
seasvacc	Numeric (binary)	0 = No 1 = Yes	Coded as yes if >14 days between seasonal vaccination and onset of symptoms.
swabdelay	Numeric (continuous)	Unique integer	Number of days between onset date of symptoms and swab date.
swabless4	Numeric (binary)	0 = No 1 = Yes	1 indicates less than 4 days between symptom onset and swab date. 0 indicates more than 3 days.
anychron	Numeric (categorical)	0 = No 1 = Yes 8 = Don't know	0 indicates no chronic disease. 1 indicates at least 1 chronic disease. 8 indicates no chronic disease reported as 'yes' and at least one chronic disease reported as 'unknown'.
smokcurr	Numeric (binary)	0 = No 1 = Yes	Current smoker (1) vs. former smoker or never-smoker (0).
hosp	Numeric (binary)	0 = No 1 = Yes	Not hospitalised for chronic disease in past 12 months (0). Hospitalized for chronic disease in past 12 months (1).
previousflu	Numeric (binary)	0 = No 1 = Yes	Vaccinated with seasonal flu in any of the two years prior to current season.
weekepi	Continuous	Integer	Week of first case coded as 1, subsequent weeks incremental.

## Syntax for one-stage pooling model:

```
// using pooled dataset with a variable for study
xi: logistic caseflu seasvacc age75 sex chronic smokcurr functional previousflu hosp gpvisit i.weekepi i.idcountry
```

Stata syntax serves as guidance only and syntax should be adapted to the given situation.

## Study-specific annexes

Study specifications for each country will be summarised in the annexes. Each study annex should include:

- description of the GPs participating in the study (number, distribution, catchment population, mode of recruitment);
- definition of beginning, peak, end of influenza season;
- ILI cases: specify if all ILI cases are recruited or a simple random or systematic sample is taken;
- criteria for selection of control groups and definition of control groups to be used;
- (**p** Seasonal and pandemic vaccines used.)
- vaccine ascertainment method;
- list of underlying conditions considered for risk groups for seasonal vaccine;
- (**b** List of underlying conditions considered for risk groups for seasonal vaccine)
- sample size calculation;
- details on methods for data collection, data entry and data transmission;
- data validation procedures;
- laboratory issues (laboratory performing tests; tests used: PCR, culture, strain characterisation; methods for specimen collection, storage, transport; selection procedures for vaccine strain characterisation);
- consent, ethical procedures (oral/written consent; submission to ethics committee, if applicable);
- human resources needed;
- provisions to train GPs;
- detailed budget;
- estimate of GPs acceptance of EpiConcept's web-based questionnaire; and
- outline of additional studies (if applicable).
